6.2.4 Pharmacokinetics (if applicable)

N/A

6.2.5 Biomarkers (if applicable)

Urine collection will be done at study intake to assess cotinine levels, illicit drug use, and pregnancy status. Urine collection will be done at Lab 1 and Lab 2 for females to determine pregnancy status. Saliva collection will be done at intake to assess nicotine/cotinine levels.

6.3 Study Procedures

Prescreening

Potential participants will be recruited via flyers, online recruitment (e.g. Yale Daily News, YCCI website, Craigslist), and/or materials with study information and phone number. PI and/or study research staff will be responsible for contacting participants. Potential participants will be directed to a voluntary link containing brief screening questions including information for research team to contact and/or phone number for participants to contact research staff directly. If interested participants will be asked if they regularly use nicotine

containing e-cigarettes, if those e-cigarettes are flavored (including flavors like tobacco), and if they are over 21. If interested, potential participants will be invited to take part in an intake visit to determine eligibility. Intake visits will be completed in person, as a urine sample is needed.

Intake Visit

Participants will be asked to complete intake in two parts; the first remotely (via Zoom) and an in person session to collect biochemical specimens. If participants do not have the necessary technology to complete the first part of the intake remotely, the full intake will be done in person. All intakes will be conducted at CMHC ([name]). At intake, participants will be consented via Redcap consent. Informed consent will be obtained while participant is in Zoom or in person. If on Zoom, participant will be instructed to be in a private setting away from others. Research staff will administer consent from a private room. If in person, consent will be obtained in a private room. Participants will have as much time as needed to consider consent.

If participant provides consent, they will provide identifying information (to be kept separately from deidentified study materials in a locked cabinet). At intake participants will complete the following assessments:

- **30-day Timeline Follow Back** assessing e-cigarette use, other tobacco product use, marijuana use, and alcohol use,
- **E-cigarette/Tobacco Use History** assessing e-cigarette use history and tobacco use history, products used, flavors tried
- **Demographic Questionnaire**
- **E-Cigarette Dependence Scale (EDS)²⁸**
- **Medical History** assessing psychiatric and medical conditions
- **Asthma Control Test,²⁹** participants will be asked to rate their asthma symptoms on a 1-5 scale, from “all of the time” to “none of the time”. This five-question health survey is used to measure asthma control in individuals 12 years and older.
- **FACIT cough questionnaire**, a single item assessing cough severity
- **PROMIS Fatigue,³⁰** we will use the 7-item PROMIS measure of fatigue which rates fatigue from 1=“never” to 5=“always”.
- **PROMIS Dyspnea,³¹** We will use the 5-item PROMIS measure of dyspnea which rates shortness of breath from 1-10. Items include: shortness of breath in general, intensity of shortness of breath, frequency of shortness of breath and duration of shortness of breath.
- **EVALI Health Assessment checklist**, a checklist of health symptoms and severity of these symptoms that could be related to nicotine exposure/vaping illness

Additionally, at the in-person portion of the intake, we will collect a urine sample and test cotinine level (a byproduct of nicotine) using a dichotomous dipstick (Countrywide Testing, 1 panel quickscreen cotinine/nicotine test dipcard – (COT200) DCT-114), illicit drug use, and if female, pregnancy. We will do a brief physical and collect blood pressure, spirometry, pulse oximetry, heart rate, and breath carbon monoxide (CO)

Lab Visits

See list of assessments in Table 1. Participants will be asked to abstain from e-cigarette use and other tobacco product use two hours prior to the session, which will be assessed via self-report. At session arrival, participants will complete baseline questionnaires (see Visit Schedule below), heart rate, blood pressure, spirometry, and pulse oximetry. After

completion of baseline assessments, at Lab 1, participants will be familiarized with the sensory and hedonic scales and trained in how to puff the e-cigarette (using non-nicotine and non-flavored e-liquid). Participants will then begin testing procedures for their assigned Flavor 1, which will be administered under double-blinded randomized conditions (see above). For each flavor, participants will take two puffs of the flavor when diluted by four levels of water concentration. Participants will be instructed to take two 3-second puffs with a 30 second inter puff interval. Each two-puff bout will be separated by 10-minutes. These procedures are adapted from our recent work (HIC #2000023077), with the number of puffs is reduced as we are not examining the effects of nicotine and only sensory effects of flavor. Per our current practice we will record timed instructions for each puff bout and participants will be trained to follow these directions. Following each puff exposure participants will complete the General Labeled Magnitude Scale (gLMS) for measures of overall intensity, irritation, coolness and sweetness, the Labeled Hedonic Scale (LHS) for measures of liking, the E-Cig Effects Questionnaire for measures of e-cigarette drug effects, and the Multiple-Choice Questionnaire to assess e-cigarette value. Participants will complete the above procedures for two flavors and four water concentrations for each flavor during each lab session. For each flavor, water concentration order will not be randomized and will be presented from hypothesize least irritating (20% water concentration) to hypothesized least irritation (e-liquid as commercially available with no water dilution) to a) maintain consistency of presentation of water concentration across flavors and b) to avoid potential irritation effects from hypothesized more irritating products to less irritating products. Following at least 24 hours, participants will repeat procedures with the remaining two flavors. Each lab session will last approximately two hours.

Debrief

At the end of Lab 2, participants will be thanked for their participation and ask to evaluate the four flavors they sampled (i.e. guess what flavors they tried, what nicotine concentration they e-liquids were) and will be given information from the CDC on e-cigarette cessation.

Table 1. List of Study Assessments

	Pre-screening (Pre-consent)	Intake	Lab 1 Baseline Assessments	Lab 1Assessments Following each E-Liquid Administration	Lab 2 Baseline Assessments	Lab 2 Assessments Following each E-Liquid Administration
Contact Info & Eligibility Review	X					
Informed Consent		X				
Identifying Information		X				
Demographics		X				
30-day Timeline Follow-back		X				
Tobacco & E-Cigarette Use History		X				
Medical History		X				
E-Cigarette Dependence Scale		X				
Cotinine & Urine Drug Screen		X				
Asthma Control Test		X	X		X	
PROMIS Fatigue		X	X		X	
PROMIS Dyspnea		X	X		X	
FACIT Cough Question		X	X		X	

EVALI Health Assessment		X	X		X	
General Labeled Magnitude Scale (gLMS)				X		X
Labeled Hedonic Scale (LHS)				X		X
E-Cigarette Drug Effects				X		X
Multiple Choice Questionnaire				X		X
Heart Rate, Blood Pressure, Pulse Oximetry		X	X		X	
Pregnancy Test		X	X		X	
Debrief						X

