Products used in our study are purchased only from a licensed retailer and do not contain CBD, THC, or Vitamin E Acetate, so the risks of developing EVALI as a result of study participation are highly unlikely. However, we will monitor for EVALI symptoms at intake and at each lab session using an assessment checklist developed in response to EVALI by our lab, the health assessment checklist (included in study measures). Any study participant reporting current THC/CBD vaping and report of mild or greater EVALI-related symptoms (i.e. cough, shortness of breath, chest pain, nausea, vomiting, stomach pain, diarrhea, fever, chills, or weight loss) without non-EVALI reasonable and proximal cause will be ineligible or withdrawn and recommended.

Additionally, e-cigarette liquids contain propylene glycol and vegetable glycerin, which some people may be allergic to. As participants are current e-cigarette users', so all participants will have prior exposure to these constituents. Additionally, we will only allow participants with experience with flavored e-liquids. We will confirm at intake they do not have known allergies to either of these products or e-liquid flavors.

(2) E-Liquid Water Manipulation: Some of the e-liquids participants will use will have water added to liquid at levels, so total water level of the e-liquid is 5% total volume, 10% of total volume, 20% total volume. Unmanipulated e-liquids contain some level of water. There is no evidence that the addition of water will produce any additional harm to e-cigarette users or that e-cigarette device will heat water to a level that produces harm.²⁰ Evidence suggests that addition of water may reduce irritation associated with e-cigarette use.

(3) Nicotine Exposure: E-liquids will contain moderate levels of nicotine salts (36mg/ml). Common side effects of nicotine include nausea, vomiting, heartburn, and elevated heart rate and blood pressure. Toxic doses of nicotine may cause abdominal pain, hypersalivation, diarrhea, dizziness, confusion, hearing and vision problems, syncope, seizures, hypotension, irregular pulse, and death. However, these toxic effects occur at doses 40 to 50 times higher than those that will be used in our studies. Moreover, by recruiting adults who already have experience with e-cigarettes and nicotine, we will further mitigate the risk of these side effects.

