E-liquid Administration/Participant Instructions/Pausing due to AEs: Participants will be administered e-liquid in an observed laboratory setting in which they are instructed to take two directed puffs of each e-liquid at each water concentration. Between 2-puff puff bouts, participants will be required to wait 10-minutes before engaging in next puff bout. Participants are not allowed to leave the site with product. There will no changes in nicotine concentration (only flavor administered) and all participants will sample all flavor/water concentration manipulations. The lab sessions will be conducted by trained research staff who are sensitive to the adolescent and smoking population and trained to monitor any potential adverse effects. Heart rate, blood pressure, and pulse oximetry will be assessed at baseline and every in-person visit for safety. If they experience any side effects or concerns during the study, we ask them to let us know. Participants will be told that they are able to stop the study at any point. If they feel any discomfort or need to stop for any reason, they can let the research team know. In the event of a serious adverse event, the PI ([name]), will consult with Yale Tobacco Center for Regulatory Science (TCORS; the funder of

this pilot) co-Is, [name] [name] and [name], along with center chemosensory expert [name] to determine if blind needs to be broken. Given all study participants are administered all e-liquids, the study will be paused during this period.

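### In each lab session, heart rate, blood pressure and pulse oximetry are scheduled only at arrival, so they cannot detect an effect of that session's nicotine; one end-of-session repeat would narrow this small gap

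*Combined protocol and SAP*

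**What the plan says.** Section 6.3 (Lab Visits) places the vital signs at the start of each session: "At session arrival, participants will complete baseline questionnaires (see Visit Schedule below), heart rate, blood pressure, spirometry, and pulse oximetry". In Table 1 the row "Heart Rate, Blood Pressure, Pulse Oximetry" is marked at Intake, Lab 1 Baseline and Lab 2 Baseline, and is blank in both columns for assessments after each e-liquid administration. The EVALI checklist follows the same schedule.

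The purpose of the readings is stated in the E-liquid Administration paragraph under section 6.1: "Heart rate, blood pressure, and pulse oximetry will be assessed at baseline and every in-person visit for safety". That sentence, and a similar one in section 6.2.3, give no time within the visit.

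Section 3.2.1 names the expected acute effects: "Common side effects of nicotine include nausea, vomiting, heartburn, and elevated heart rate and blood pressure".

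During the session the protocol relies on staff who are "trained to monitor any potential adverse effects" and on self-report: "If they experience any side effects or concerns during the study, we ask them to let us know". The scheduled assessments after each bout are the gLMS, the LHS, the E-Cig Effects questionnaire and the Multiple Choice Questionnaire. Sections 6.3 and 6.3.1 put at least 24 hours between the sessions, and section 6.3.6 plans no follow-up after the second.

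**The concern.** A reading taken for safety in a nicotine exposure study should be able to show a response to the exposure. Here it is taken after a requested two hours of abstinence and before the session's first nicotine puff. It can screen out someone who arrives unwell, but it cannot register what the puffs do.

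Two of the five side effects that the protocol calls common, raised heart rate and raised blood pressure, can occur without symptoms. A participant could leave with either one unmeasured. The other three (nausea, vomiting, heartburn) are recorded only if volunteered or noticed. The causality categories in section 6.2.3 also depend on a credible time relation to administration, and a timed reading after puffing, set against the same day's arrival value, would help to establish one.

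What is at stake is the completeness of safety observation, not the efficacy conclusions.

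**Working it through.** **Exposure, reproducing the plan's figure.** Inputs are four flavors, four water levels and two puffs per combination (sections 5.1 and 6.3).
- Whole study: 4 × 4 × 2 = 32 puffs. Per session: 2 flavors × 4 levels × 2 puffs = 16. Both match section 3.2.1.
- Section 6.2.1 (item 4) offers a choice at session end that may bring 10 more puffs: 16 + 10 = 26. The range is therefore 16 to 26 puffs per session.

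**Scheduled vital signs per participant** (Lab Visits text and Table 1).
- Now: intake + Lab 1 arrival + Lab 2 arrival = 3. Between the first puff and leaving a session: 0.
- The Lab 2 arrival reading comes at least 24 hours after Lab 1, so it can show only what persists. No scheduled reading follows the Lab 2 puffs.

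**Do the scheduled post-bout measures fill the gap?**
- The E-Cig Effects questionnaire has 4 liking/wanting + 2 stimulant + 6 withdrawal = 12 items. None is nausea, vomiting, heartburn, heart rate or blood pressure.
- The gLMS rates intensity, irritation, coolness and sweetness. The LHS rates liking, and the Multiple Choice Questionnaire rates monetary value.
- So 0 of the 5 named side effects have a scheduled post-puff item.

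**Effect of one end-of-session repeat.**
- Readings per participant: 3 + 2 = 5, of which 2 follow puffing.
- Added checks if all complete: 30 × 2 = 60.
- Staff time at an assumed 5 to 10 minutes each: 60 × 5 = 300 min = 5 h, to 60 × 10 = 600 min = 10 h.

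**What one reading can still miss.** Each bout lasts 3 + 30 + 3 = 36 s = 0.6 min. With 10 minutes between bouts the cycle is 10.6 min. Bout 1 ends at 0.6 min, bout 7 at 6 × 10.6 + 0.6 = 64.2 min, and bout 8 at 7 × 10.6 + 0.6 = 74.8 min. Assume that the last ratings take 0 to 10 minutes and that no optional puffs are taken. The reading then falls:
- 0 to 10 min after bout 8;
- 10.6 to 20.6 min after bout 7;
- 74.2 to 84.2 min after bout 1.

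For anyone who takes the optional puffs the reading is later relative to all eight bouts, by an amount that the protocol does not fix.

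**The case against.** The strongest reply is that this is a reasoned choice. Participants are regular users with urine cotinine of at least 200 ng/mL, and significant cardiovascular and pulmonary conditions are excluded (section 5.3.2). Bouts are two puffs, 10 minutes apart. The FDA reviewed the product use and raised no concerns (section 6.1.1). A DSMB reviews the plans before the start and every six months (section 7.12). Sessions are observed, and nausea or vomiting would probably be seen or reported. All of this stands, and it makes harm unlikely. None of it measures a symptom-free rise after puffing. The safety margin in section 3.2.1, "these toxic effects occur at doses 40 to 50 times higher than those that will be used in our studies", refers to toxic effects and not to the common side effects.

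Table 1 is also imperfect corroboration. It omits spirometry, which the text schedules at arrival, and it has no end-of-session column. The point therefore rests mainly on the Lab Visits text, which is clear.

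Three stronger readings are tempting, and the documents do not support them:
- **The protocol breaks its own promise.** It does not. One reading at arrival satisfies a reading at every in-person visit.
- **Nothing is monitored once puffing starts.** Observation and self-report are both specified.
- **The EVALI checklist should simply be repeated.** It is described as "a checklist of health symptoms and severity of these symptoms that could be related to nicotine exposure/vaping illness", but its items and recall window are not reproduced, so its coverage of the five side effects cannot be counted. The EVALI-related symptoms in section 5.3.2 include weight loss, fever and chills, which hardly suit a two-hour window. Cough and shortness of breath may overlap with the irritation under study.

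**Conclusion.** The point holds as a minor design improvement. The schedule is established by the text: 3 vital-sign readings per participant, 0 of them after puffing within a session, against 16 to 26 puffs per session. The benefit of changing it is less certain. The documents give no rate of unreported or symptom-free effects, so any number of affected sessions would only be an assumed rate multiplied by 60. A single end reading narrows the gap and does not close it, because it can miss short-lived rises after earlier bouts. The staff-time figure rests on the assumed 5 to 10 minutes per check.

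**What to change.** In the Lab Visits text and Table 1, add one end-of-session repeat of heart rate, blood pressure and pulse oximetry at Lab 1 and Lab 2, taken after the last ratings and after any optional puffs. Add a short direct question on nausea, vomiting and heartburn since the first puff that day, in place of the full EVALI checklist. Compare the values with that session's arrival reading.

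Set simple limits for concern in advance, allowing for the rise in heart rate and blood pressure that section 3.2.1 already expects. If a value is outside them, repeat it before the participant leaves, and contact the study physician mentioned in section 6.2.3 only if it persists.

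The cost is a minor amendment and 5 to 10 staff hours over 60 checks on the stated assumption. Physician time for occasional calls and some delayed departures come on top and are not costed here. Staff and equipment for the vital signs are already in place. The check follows the session's final ratings, so it cannot disturb them.

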6.3.1 Study Schedule

Participants will participate in an intake visit (that will be completed in two parts; remote and in-person as possible). Following intake, they will complete two lab sessions approximately 2 hours each that occur at least 24 hours apart.

6.3.2 Informed Consent

At intake, participants will be read informed consent and any questions will be discussed with researcher. Participants will sign informed consent (via Redcap) and consent will be administered by trained research staff.

6.3.3 Screening

Prescreening

Potential participants will be recruited via flyers, online recruitment (e.g. Yale Daily News, YCCI website, Craigslist), and/or materials with study information and phone number. Potential participants will be directed to a voluntary link and/or phone number. If interested, participants will be asked if they regularly use nicotine containing e-cigarettes, if those cigarettes are flavored (including flavors like tobacco), and if they are over 21. If interested, potential participants will be invited to take part in an intake visit to determine eligibility.

6.3.4 Enrollment

If eligibility criteria is met, participant will be enrolled. PI ([name]) will deem subjects eligible following review and will assign enrolled subject ID.

6.3.5 On Study Visits

See 6.3 "Study Procedures" above for detailed description of on study (Lab 1 & 2) procedures and assessments administered in Table 1.

6.3.6 End of Study and Follow-up

After study completion, participants will be given written material for cessation. Given low study risk and brief e-cigarette administrations, no follow up sessions will occur.

6.3.7 Removal of subjects

Subjects may withdraw at time voluntarily for any reason. Once participants have signed consent, they may withdraw at any time by communicating to any member of the research team. Any data that has already been collected can still be used, as necessary to ensure the integrity of the study and/or study oversight. Additionally, the research team may decide to withdraw participants if necessary including if participants do not follow directions of the study team, the study team decides the study is not in a participant's best interest, or if a participant becomes pregnant, intends to become pregnant, or begins nursing a child.

No anticipated adverse events are expected that would require participant withdrawal. Adverse events are not anticipated. In the event that a participant either withdraws from the

study or the investigator decides to discontinue a participant due to an adverse event, the participant will be monitored by the investigator via ongoing status assessment until 1) a resolution is reached i.e., the problem requiring hospitalization has resolved or stabilized with no further changes expected 2) the SAE is determined to be clearly unrelated to the study intervention, or 3) the SAE results in death. Outcome of SAEs will be periodically reported to NIDA. A summary of the SAEs that occurred during the previous year will be included in the annual progress report to NIDA. Withdrawal will be documented in a study participant tracker.

6.4 Statistical Method

6.4.1 Statistical Design

To examine the primary objective of the study, which is to examine how increasing the concentration of e-liquids with aldehyde flavor chemicals impacts sensory perception of irritation and appeal among current adult e-cigarette users, we will use mixed effects models with water concentration as the within subject factor and each of the measure (e.g. irritation, appeal) as outcomes in separate models. Outcome analyses will be intent-to-treat and using mixed-effects models. These models allow for different numbers of observations per subject, use all available data, and can handle missing-at-random data. If model assumptions will appear to be violated, we will transform the data or fit more flexible generalized linear or nonparametric mixed models. A significant main effect of condition will be considered supportive of our hypothesis. We will construct confidence intervals for least square means and contrasts between least square means to estimate effect sizes and to inform future studies.

For the secondary aim, which is to examine differences by flavor for outcomes at each water concentration, we will examine at each water concentration, flavor as the within subject factor and each of the measure (e.g. irritation, appeal) as outcomes in separate models. We will construct confidence intervals for least square means and contrasts between least square means to estimate effect sizes and to inform future studies.

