4.1 Hypothesis

We hypothesized that as total water volume is increased in nicotine e-liquids containing flavor aldehydes, sensory irritation experienced by the e-cigarette user will decrease. We do not expect to see this decrease in the control e-liquid (grape e-liquid), which does not contain flavor aldehydes.

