5.3.1 Number of Participants

The current study is a pilot study and we aim to enroll 30 subjects. Based on previous pilot experimental work with e-cigarettes in our group, 30 has been sufficient for by our biostatistical staff for determining large effects by water level.

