6.1.4 Method of Assignment/Randomization

All participants will receive every flavor/water concentration (4 e-liquids flavors at 4 water concentrations = 16 total manipulations). Participants and research assistants will be blinded to flavors administered. We will use block randomization to determine order flavors are presented in. Water concentration will be presented from hypothesized least irritating to most irritating (20% water, 10% water, 5% water, no alteration).

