6.4.2 Sample Size Considerations

Given this is a pilot study, formal power analyses were not conducted. However, based on prior pilot data in which brief lab exposure to e-cigarettes were conducted by our group (HIC 2000025687) determined that 30 participants is sufficient to detect large differences of irritation and appeal by water concentration at two sided alpha level of 0.05.

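### The rule for declaring support has no direction and leaves out the grape control, although the hypothesis is a decrease in irritation in aldehyde flavors only

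*Combined protocol and SAP*

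**What the plan says.** Section 4.1 has two parts. As water is added to aldehyde e-liquids, "sensory irritation experienced by the e-cigarette user will decrease". For the control, "We do not expect to see this decrease in the control e-liquid (grape e-liquid), which does not contain flavor aldehydes". Section 4.2 likewise frames the primary objective as a comparison of the aldehyde flavors with grape.

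The analysis in section 6.4.1 uses "mixed effects models with water concentration as the within subject factor", with a separate model for each outcome. The criterion follows: "A significant main effect of condition will be considered supportive of our hypothesis". Section 6.5.1 repeats it. Neither section attaches a direction, an ordering of the levels or a comparison with grape. The next sentence plans confidence intervals for least square means and their contrasts, but to estimate effect sizes and guide later studies, not as part of the criterion.

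The design is "4 e-liquids flavors at 4 water concentrations = 16 total manipulations" (section 6.1.4). Section 6.4.2 gives a "two sided alpha level of 0.05" and says that "30 participants is sufficient to detect large differences of irritation and appeal by water concentration", without a power figure, an effect size, a standard deviation or a correlation.

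**The concern.** The criterion and the hypothesis do not match in two respects.

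- **Direction.** A main effect is significant whenever the four water levels differ enough, whichever way they differ.
- **Control.** No term in the described primary model compares the water effect in the aldehyde flavors with that in grape. If the model pools all four flavors, grape simply contributes to the average. If it uses the aldehyde flavors alone, grape is absent.

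The second gap matters more because section 6.1.4 fixes the order of water levels within every flavor (20%, 10%, 5%, native). Water level and position in the sequence are therefore confounded. Build-up of or adaptation to irritation that is common to all flavors would appear as a water effect in each of them. The grape comparison is the part of the design that can subtract such a shared effect, and the criterion does not use it.

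At stake is what the trial may claim. Section 3.2.2 says that the results could inform rules on water content.

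**Working it through.** **Inputs.** From the documents: n = 30, four water levels, two-sided alpha 0.05. Inferred: water is categorical, since the text calls it a factor and summarises it by least square means, which gives 3 numerator df and 3 × 29 = 87 error df. The documents state neither coding nor df. Effect sizes and correlations below are assumptions.

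**1. The plan's own figure.** The statement that 30 is enough for large differences cannot be reproduced. As a plausibility check, take f = 0.4 as large and λ = n·k·f²/(1 − ρ). With ρ = 0, λ = 30 × 4 × 0.16 = 19.2 and F(3,87) has 96.2% power. With ρ = 0.3, λ = 27.43 and power is 99.5%. The statement is plausible but unverified.

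**2. Direction.** For level means μⱼ, the noncentrality is λ = n·Σ(μⱼ − μ̄)²/σ². Reversing the sign of every deviation leaves λ unchanged, so a fall and an equal rise have the same chance of meeting the criterion. This was simulated with 200,000 trials per pattern, each non-null pattern scaled to λ = 11.40 (80% power). The comparator is a linear contrast with scores −3, −1, 1, 3 and 29 df, significant at two-sided 0.05 and in the decreasing direction.

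| True pattern (native, 5, 10, 20%) | Plan's rule declares support | Directional contrast declares a decrease |
|---|---|---|
| Decrease (3, 2, 1, 0) | 80.0% | 90.4% |
| Increase (0, 1, 2, 3) | 80.0% | 0.0% |
| Zigzag (0, 1, 0, 1) | 80.0% | 0.03% |
| Inverted U (0, 1, 1, 0) | 80.0% | 2.5% |
| No effect | 5.0% | 2.5% |

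With no effect, about half of the rule's 5.0% (2.5 points) comes with a rising slope, and only 0.2 points show a steady decrease across all four levels.

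**3. Control.** Let δA and δG be the water effects in the aldehyde flavors and in grape. If δA = δG ≠ 0, the main effect is real and the rule reports support, yet δA − δG = 0 and the second part of section 4.1 is false.

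The comparison costs precision. Let each flavor's contrast have variance v, and let contrasts in different flavors be independent. The mean of three aldehyde contrasts then has variance v/3, and its difference from grape has v/3 + v = 4v/3, four times as much. With grape flat, an aldehyde contrast with 80% power (λ = 8.03, 87 df) corresponds to λ = 8.03/4 = 2.01 for the difference, and about 29% power. If a participant's contrasts correlate at r across flavors, the ratio becomes 4(1 − r)/(1 + 2r): 4 at r = 0 and 1 at r = 0.5. The documents give no r.

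**4. Power of a 1-df trend against the 3-df test** (exactly linear decline, same λ, 87 error df):

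| λ | 3-df test | 1-df trend | Gain (points) |
|---|---|---|---|
| 6.02 | 50% | 68% | 18 |
| 7.48 | 60% | 77% | 17 |
| 9.20 | 70% | 85% | 15 |
| 11.40 | 80% | 92% | 12 |
| 19.2 (f = 0.4, ρ = 0) | 96.2% | 99.1% | 2.9 |
| 27.43 (f = 0.4, ρ = 0.3) | 99.5% | 99.9% | 0.4 |

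If all the benefit comes by 5% water and then levels off, the trend loses. Scores −3, −1, 1, 3 retain 9/(20 × 0.75) = 0.60 of λ = 11.40, giving 73.5% against 80%. Scores in percent water, with native at 1% (the worked example in section 6.1.3) and centered at −8, −4, 1, 11, retain 64/(202 × 0.75) = 0.42, giving 58%.

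**The case against.** The best defence is the sentence after the criterion. Intervals for level means and contrasts would show any reader which way irritation moved, and an investigator who saw a rise would be unlikely to call it support. It is also a pilot: "The current study is a pilot study and we aim to enroll 30 subjects". This makes a misreport improbable, so the documents do not support the inference that a rise would in fact be presented as a success. The rule itself stays wrong, because those contrasts have no part in it, and showing direction within flavors still leaves grape untested.

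Three stronger readings are tempting, and none is supported.

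- **The 3-df test wastes substantial power.** Section 6.4.2 speaks only of large differences. At f = 0.4 the loss is about 3 points or less, and the 3 df are themselves an inference.
- **The rule must become a linear slope.** The outcomes in section 5.2.1 are changes at each water level, and sections 2.2 and 3.2.2 have a fixed or minimum level in mind. Level contrasts serve that as well as a slope does or better, and the slope loses up to 22 points (80% to 58%) under a plateau.
- **The plan treats a fall in appeal as support.** The sentence covers the appeal models only by its position. The sole hypothesis, in section 4.1, concerns irritation, and appeal might also rise. What stands is that the sentence does not say which outcome it governs.

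**Conclusion.** The concern holds for direction and for the control. The criterion in sections 6.4.1 and 6.5.1 can be met by results that contradict section 4.1: a rise, an irregular pattern, or the same change in aldehyde flavors and grape. This follows from the form of the test and needs no assumption about effect size; the 80% in the simulation only shows that the rule treats all patterns of equal size alike. The numbers rest on categorical coding, 87 error df for the 3-df test and independent, equal-variance errors. Any power gain from a trend contrast depends on the shape and size of the effect and is not a reason in itself to change the plan. The correction should be made before outcome data are analysed.

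**What to change.** In both sections, replace the criterion with wording such as: *Support requires gLMS irritation to be lower with added water in the aldehyde flavors, shown by a prespecified contrast among least square means that is significant at two-sided 0.05 in the decreasing direction. For the primary objective, the aldehyde-minus-grape difference in that contrast will be tested.*

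- Name the contrast in advance: either an ordered trend with stated scores, or added-water levels against native with multiplicity control.
- Keep the overall water test as supportive; it guards against missing a plateau.
- State that the sentence applies to irritation only. Judge appeal separately, against the aim in section 3.2 of not adversely affecting it, and say what direction and size of change would count as adverse.

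**Cost.** Wording only; data collection, sample size and procedures do not change. There are two statistical costs. The aldehyde-minus-grape contrast is less precise than the aldehyde-only contrast unless a participant's contrasts correlate strongly across flavors, so with 30 participants its interval should be reported whatever the test shows. A trend contrast, if chosen, has less power under a plateau. A directional rule does not remove the confounding of water level with order; the grape comparison removes only the part shared by all flavors.
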